11.1.4 Response Criteria

11.1.4.1 Evaluation of Target Lesions

Complete Response (CR): Disappearance of all target lesions. Any pathological lymph nodes (whether target or non-target) must have reduction in short axis to <10 mm.

Partial Response (PR): At least a 30% decrease in the sum of the diameters of target lesions, taking as reference the baseline sum diameters.

Progressive Disease (PD): At least a 20% increase in the sum of the diameters of target lesions, taking as reference the smallest sum on study (this includes the baseline sum if that is the smallest on study). In addition to the relative increase of 20%, the sum must also demonstrate an absolute increase of at least 5 mm. (Note: the appearance of one or more new lesions is also considered progressions).

Stable Disease (SD): Neither sufficient shrinkage to qualify for PR nor sufficient increase to qualify for PD, taking as reference the smallest sum diameters while on study.

11.1.4.2 Evaluation of Non-Target Lesions

Complete Response (CR): Disappearance of all non-target lesions and normalization of tumor marker level. All lymph nodes must be non-pathological in size (<10 mm short axis).

Note: If tumor markers are initially above the upper normal limit, they must normalize for a patient to be considered in complete clinical response.

Non-CR/Non-PD: Persistence of one or more non-target lesion(s) and/or maintenance of tumor marker level above the normal limits.

Progressive Disease (PD): Appearance of one or more new lesions and/or *unequivocal progression* of existing non-target lesions. *Unequivocal progression* should not normally trump target lesion status. It must be representative of overall

disease status change, not a single lesion increase.

Although a clear progression of “non-target” lesions only is exceptional, the opinion of the treating physician should prevail in such circumstances, and the progression status should be confirmed at a later time by the review panel (or Principal Investigator).

11.1.4.3 Evaluation of Best Overall Response

The best overall response is the best response recorded from the start of the treatment until disease progression/recurrence (taking as reference for progressive disease the smallest measurements recorded since the treatment started). The patient's best response assignment will depend on the achievement of both measurement and confirmation criteria.

For Patients with Measurable Disease (*i.e.*, Target Disease)

| Target Lesions | Non-Target Lesions | New Lesions | Overall Response | Best Overall Response when Confirmation is Required* |
|---|-----------------------------|-------------|------------------|--|
| CR | CR | No | CR | ≥4 wks. Confirmation** |
| CR | Non-CR/Non-PD | No | PR | ≥4 wks. Confirmation** |
| CR | Not evaluated | No | PR | |
| PR | Non-CR/Non-PD/not evaluated | No | PR | |
| SD | Non-CR/Non-PD/not evaluated | No | SD | documented at least once ≥4 wks. from baseline** |
| PD | Any | Yes or No | PD | no prior SD, PR or CR |
| Any | PD*** | Yes or No | PD | |
| Any | Any | Yes | PD | |
| 
* See RECIST 1.1 manuscript for further details on what is evidence of a new lesion.
 
** Only for non-randomized trials with response as primary endpoint.
 
*** In exceptional circumstances, unequivocal progression in non-target lesions may be accepted as disease progression.
 
Note: Patients with a global deterioration of health status requiring discontinuation of treatment without objective evidence of disease progression at that time should be reported as “symptomatic deterioration.” Every effort should be made to document the objective progression even after discontinuation of treatment.
 | | | | |

For Patients with Non-Measurable Disease (i.e., Non-Target Disease)

| Non-Target Lesions | New Lesions | Overall Response |
|--------------------|-------------|------------------|
| CR | No | CR |
| Non-CR/non-PD | No | Non-CR/non-PD* |
| Not all evaluated | No | not evaluated |
| Unequivocal PD | Yes or No | PD |
| Any | Yes | PD |

* 'Non-CR/non-PD' is preferred over 'stable disease' for non-target disease since SD is increasingly used as an endpoint for assessment of efficacy in some trials so to assign this category when no lesions can be measured is not advised

11.1.5 Duration of Response

Duration of overall response: The duration of overall response is measured from the time measurement criteria are met for CR or PR (whichever is first recorded) until the first date that recurrent or progressive disease is objectively documented (taking as reference for progressive disease the smallest measurements recorded since the treatment started).

The duration of overall CR is measured from the time measurement criteria are first met for CR until the first date that progressive disease is objectively documented.

Duration of stable disease: Stable disease is measured from the start of the treatment until the criteria for progression are met, taking as reference the smallest measurements recorded since the treatment started, including the baseline measurements.

11.1.6 Progression-Free Survival

PFS is defined as the duration of time from randomization to time of progression or death, whichever occurs first.

12. DATA REPORTING / REGULATORY REQUIREMENTS

Adverse event lists, guidelines, and instructions for AE reporting can be found in [Section 7.0](#) (Adverse Events: List and Reporting Requirements).

12.1 Data Reporting

12.1.1 Method

This study will be monitored by the Clinical Data Update System (CDUS) version 3.0. Cumulative CDUS data will be submitted quarterly to CTEP by electronic means. Reports are due January 31, April 30, July 31, and October 31. Instructions for submitting data using the CDUS can be found on the CTEP web site (<http://ctep.cancer.gov>). **Note:** All adverse events that have occurred on the study, including those reported through CTEP-AERS, must be reported via CDUS.

12.1.2 Responsibility for Data Submission

Study participants are responsible for submitting CDUS data and/or data forms to the

Coordinating Center quarterly to allow time for Coordinating Center compilation, Principal Investigator review, and timely submission to CTEP (see [Section 12.1.1.](#)).

The Coordinating Center is responsible for compiling and submitting CDUS data to CTEP for all participants and for providing the data to the Principal Investigator for review.

12.2 CTEP Multicenter Guidelines

This protocol will adhere to the policies and requirements of the CTEP Multicenter Guidelines. The specific responsibilities of the Principal Investigator and the Coordinating Center (Study Coordinator) and the procedures for auditing are presented in [Appendix B](#).

- The Principal Investigator/Coordinating Center is responsible for distributing all IND Action Letters or Safety Reports received from CTEP to all participating institutions for submission to their individual IRBs for action as required.
- Except in very unusual circumstances, each participating institution will order DCTD-supplied agents directly from CTEP. Agents may be ordered by a participating site only after the initial IRB approval for the site has been forwarded by the Coordinating Center to the CTEP PIO ([contact]) except for Group studies.

12.3 Collaborative Agreements Language

The agent(s) supplied by CTEP, DCTD, NCI used in this protocol is/are provided to the NCI under a Collaborative Agreement (CRADA, Agent-CRADA, CTA, CSA) between the Pharmaceutical Company(ies) (hereinafter referred to as a “Collaborator(s)”) and the NCI Division of Cancer Treatment and Diagnosis. Therefore, the following obligations/guidelines, in addition to the provisions in the “Intellectual Property Option to Collaborator” (<http://ctep.cancer.gov/industry>) contained within the terms of award, apply to the use of the Agent(s) in this study:

1. Agent(s) may not be used for any purpose outside the scope of this protocol, nor can Agent(s) be transferred or licensed to any party not participating in the clinical study. Collaborator(s) data for Agent(s) are confidential and proprietary to Collaborator(s) and shall be maintained as such by the investigators. The protocol documents for studies utilizing investigational Agents contain confidential information and should not be shared or distributed without the permission of the NCI. If a copy of this protocol is requested by a patient or patient’s family member participating on the study, the individual should sign a confidentiality agreement. A suitable model agreement can be downloaded from: <http://ctep.cancer.gov>.
2. For a clinical protocol where there is an investigational Agent used in combination with (an)other investigational Agent(s), each the subject of different collaborative agreements , the

access to and use of data by each Collaborator shall be as follows (data pertaining to such combination use shall hereinafter be referred to as “Multi-Party Data”):

- a. NCI will provide all Collaborators with prior written notice regarding the existence and nature of any agreements governing their collaboration with NIH, the design of the proposed combination protocol, and the existence of any obligations that would tend to restrict NCI's participation in the proposed combination protocol.
 - b. Each Collaborator shall agree to permit use of the Multi-Party Data from the clinical trial by any other Collaborator solely to the extent necessary to allow said other Collaborator to develop, obtain regulatory approval or commercialize its own investigational Agent.
 - c. Any Collaborator having the right to use the Multi-Party Data from these trials must agree in writing prior to the commencement of the trials that it will use the Multi-Party Data solely for development, regulatory approval, and commercialization of its own investigational Agent.
3. Clinical Trial Data and Results and Raw Data developed under a Collaborative Agreement will be made available exclusively to Collaborator(s), the NCI, and the FDA, as appropriate and unless additional disclosure is required by law or court order. Additionally, all Clinical Data and Results and Raw Data will be collected, used, and disclosed consistent with all applicable federal statutes and regulations for the protection of human subjects including, if applicable, the *Standards for Privacy of Individually Identifiable Health Information* set forth in 45 C.F.R. Part 164.
 4. When a Collaborator wishes to initiate a data request, the request should first be sent to the NCI, who will then notify the appropriate investigators (Group Chair for Cooperative Group studies, or PI for other studies) of Collaborator's wish to contact them.
 5. Any data provided to Collaborator(s) for Phase 3 studies must be in accordance with the guidelines and policies of the responsible Data Monitoring Committee (DMC), if there is a DMC for this clinical trial.
 6. Any manuscripts reporting the results of this clinical trial must be provided to CTEP by the Group office for Cooperative Group studies or by the principal investigator for non-Cooperative Group studies for immediate delivery to Collaborator(s) for advisory review and comment prior to submission for publication. Collaborator(s) will have 30 days from the date of receipt for review. Collaborator shall have the right to request that publication be delayed for up to an additional 30 days in order to ensure that Collaborator's confidential and proprietary data, in addition to Collaborator(s)'s intellectual property rights, are protected. Copies of abstracts must be provided to CTEP for forwarding to Collaborator(s) for courtesy review as soon as possible and preferably at least three (3) days prior to submission, but in any case, prior to presentation at the meeting or publication in the proceedings. Press releases and other media presentations must also be forwarded to CTEP prior to release. Copies of any manuscript, abstract and/or press release/ media presentation should be sent to:

Regulatory Affairs Branch, CTEP, DCTD, NCI

13. STATISTICAL CONSIDERATIONS

13.1 Study Design/Endpoints

This is an open-label, multi-center, randomized phase II study. Patients will be randomized using 2:1 ratio to receive either MK2206 or everolimus. The primary endpoint of the study is progression-free survival (PFS), where an event is defined as either disease progression or death. The anticipated median PFS is 4.9 months and 8.2 months for the everolimus and MK2206 arms, respectively. The secondary endpoints include safety, overall survival (OS), overall response rate (ORR) and time to failure (TTF). For the primary endpoint, one interim futility analysis will be performed when a total of 38 events have occurred. The O'Brien-Fleming stopping boundaries using Lan-DeMets spending function will be used for early rejection of H1 (futility boundaries). At the interim look, if the nominal critical point (Z-scale) is less than 0.051, we will terminate trial, reject H1, and conclude that MK2206 has no significant effect on improving PFS. Assuming that the alternative hypothesis holds and trial is continued to completion without interim analysis, 105 patients with 75 events provide 81% power to reject null hypothesis. Since this trial has one interim analysis, 105 patients with 75 events provide 80% power to reject null hypothesis. Please see the detail information for power calculation in [section 13.2](#) sample size / power calculation.

Additionally, toxicity will be monitored for the MK2206 arm. For the purpose of implementing this safety rule, toxicity will be defined as Grade 3 or greater toxicity that requires treatment discontinuation. The method of Thall, Simon and Estey (1995, 1996) will be used. Denoting the probability of toxicity by p , the trial will be stopped early if for the MK2206 arm, $\text{Prob}(p > 0.30 | \text{data}) > .93$. That is, if at any time during the trial, we determine that there is more than 93% chance that the toxicity rate for the MK2206 arm is greater than 30%, we will stop the trial. Assuming a $\text{beta}(0.6, .14)$ priori for p , the above decision criterion implies that we will stop the trial if $[\# \text{ patients with toxicities in the MK2206 arm}] / [\# \text{ patients evaluated in the MK2206 arm}] \geq 3/4, 4/5, 5/7, 6/9, 7/12, 8/14, 9/17, 10/20, 11/22, 12/25, 13/28, 14/30, 15/33, 16/36, 17/39, 18/42, 19/44, 20/47, 21/50, 22/53, 23/56, 24/59, 25/62, 26/65, 27/68$. The operating characteristics for this toxicity monitoring rule are illustrated in [Table 6](#).

Table 6. Operating Characteristics for Toxicity Monitoring Rule.

| True toxicity rate | Prob (stop the trial early) | Sample Size 25 th , 50 th and 75 th percentiles |
|--------------------|-----------------------------|---|
|--------------------|-----------------------------|---|

| | | |
|------|-------|------------|
| 0.10 | 0.005 | 70, 70, 70 |
| 0.20 | 0.047 | 70, 70, 70 |
| 0.30 | 0.288 | 41, 70, 70 |
| 0.40 | 0.784 | 8, 24, 61 |
| 0.50 | 0.990 | 4, 10, 19 |

This study will be monitored by the MDACC DSMB.

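### The beta(0.6, .14) prior stated for the toxicity stopping rule does not produce the printed stopping bounds or Table 6

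*Combined protocol and SAP*

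**What the plan says.** Section 13.1 (Study Design/Endpoints) monitors toxicity on the MK-2206 arm, defined there as grade 3 or greater toxicity that requires treatment discontinuation. The trial stops if Prob(p > 0.30 | data) > .93, which the text restates as "more than 93% chance that the toxicity rate for the MK2206 arm is greater than 30" per cent. The rule applies "if at any time during the trial", and no first look is named.

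The prior is given once: "Assuming a $\text{beta}(0.6, .14)$ priori for p". The text then says that "the above decision criterion implies that we will stop the trial if" the ratio of toxicities to evaluated patients reaches one of 25 listed bounds. The list begins "3/4, 4/5, 5/7, 6/9, 7/12, 8/14, 9/17, 10/20, 11/22, 12/25" and ends at 27/68.

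Table 6 gives the operating characteristics (true rate, probability of stopping early, sample-size quartiles). Two of its rows read "0.30 | 0.288 | 41, 70, 70" and "0.50 | 0.990 | 4, 10, 19". Section 13.2 puts 70 patients on the MK-2206 arm.

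**The concern.** A beta(0.6, .14) prior has mean 0.6/0.74 = 0.81. It puts probability 0.887 on a toxicity rate above 30% before anyone is treated, close to the .93 stopping cut-off. Such a prior should stop after very little data, yet the printed list does not begin until three toxicities in four patients.

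This is the only trial-level safety stopping rule in the protocol. It is written as a posterior criterion, with the bounds presented as its consequence. If the prior and the bounds disagree, the text contains two different rules. A monitoring program built from the prior would not have the properties in Table 6.

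**Working it through.** **Inputs.** From section 13.1: prior beta(a, b) = beta(0.6, 0.14), toxicity limit 0.30, cut-off 0.93, the 25 printed bounds, and Table 6. From section 13.2: a maximum of 70 patients on the arm.

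**Formula.** With x toxicities in n patients, P(p > 0.30 | x, n) = 1 − BetaCDF(0.30; a + x, b + n − x). The bound at n is the smallest x for which this exceeds 0.93. Stopping probabilities and sample-size quartiles come from an exact forward recursion over n = 1 to 70, with a look after each patient.

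**Step 1: the printed bounds against Table 6.** Each printed count is carried forward until the next listed n (3 at n = 4, 4 at n = 5–6, 5 at n = 7–8, ..., 27 at n = 68–70). The resulting probabilities are in the second row of the table in step 3. The largest gap from Table 6 is 0.797 against 0.784 at a true rate of 0.40, or 0.790 if a stop at patient 70 is not counted as early. The list and the table belong together.

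**Step 2: the stated prior against the printed bounds.**

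| n | Printed bound | Posterior one toxicity below the printed bound, stated prior | Smallest x that stops, stated prior |
|---|---|---|---|
| 4 | 3 | below 0.93 | 3 |
| 5 | 4 | 0.948 | 3 |
| 7 | 5 | 0.954 | 4 |
| 68 | 27 | 0.935 | 26 |

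Only 3/4 matches. At each of the other 24 listed n the stated prior stops one toxicity earlier. Over every n from 4 to 70, the two rules differ at 29 of 67 sample sizes, always by exactly one toxicity.

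Before the list begins, the stated prior gives a posterior of 0.983 at 1/1 and 0.947 at 2/3, so it stops at both.

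**Step 3: the probability of stopping.**

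| Rule | 0.10 | 0.20 | 0.30 | 0.40 | 0.50 |
|---|---|---|---|---|---|
| Table 6 | 0.005 | 0.047 | 0.288 | 0.784 | 0.990 |
| Printed bounds, carried forward | 0.0045 | 0.048 | 0.283 | 0.797 | 0.991 |
| Stated prior, looks from n = 4 | 0.010 | 0.089 | 0.375 | 0.843 | 0.994 |
| Stated prior, looks from n = 1 | 0.111 | 0.260 | 0.525 | 0.884 | 0.995 |

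Sample-size quartiles:

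| True rate | Table 6 | Printed bounds | Stated prior from n = 4 | Stated prior from n = 1 |
|---|---|---|---|---|
| 0.30 | 41, 70, 70 | 48, 70, 70 | 14, 70, 70 | 1, 42, 70 |
| 0.40 | 8, 24, 61 | 8, 24, 60 | 5, 14, 45 | 1, 5, 28 |
| 0.50 | 4, 10, 19 | 4, 10, 19 | 4, 5, 14 | 1, 1, 9 |

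**Step 4: could something other than the prior be wrong?** With beta(0.6, 0.14) kept, cut-offs from 0.85 to 0.995 and toxicity limits from 0.20 to 0.40 were tried. None gave all 25 bounds; the best was 24, at a cut-off of 0.96, and that rule still matched the carried-forward list at only 43 of the 67 sample sizes.

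With the cut-off at 0.93 and the prior changed to beta(0.6, 1.4), whose mean is 0.6/2.0 = 0.30, all 25 bounds appear and the rule equals the carried-forward list at every n from 4 to 70. That prior is a one-place decimal shift from the printed one.

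It is not the only candidate. A grid search (a from 0.05 to 2.00, b from 0.05 to 3.00, step 0.05) found 18 priors with the same bounds from n = 4, with means from 0.11 to 0.30. Beta(0.6, 1.4) is the only one of them with a = 0.6. Off that grid, the swapped form beta(0.14, 0.6) also works.

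**Step 5: the first look.** Beta(0.6, 1.4) also crosses at 3/3 (0.976), which is not printed; so do the other 17 grid priors. None of them explains a list that starts at 3/4 unless looks begin at n = 4.

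**The case against.** The strongest reply is that the bounds are printed, can be used as they stand, and match Table 6. Nothing in the protocol says that the board or a program will recompute the posterior, and a board working from the list is unaffected. That stands, and it limits the severity.

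The figure 0.525 owes much to stops at 1/1 and 2/3, before the list begins. The like-for-like figure from n = 4 is 0.375. That is also fair, although 0.525 is what the wording gives when it allows a stop at any time and names no first look. The error also runs in the cautious direction: it risks an unneeded stop and does not weaken protection.

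The count of 1 in 25 sounds worse than the distance between the rules. The listed n are the steps of the boundary, so a small shift misses nearly all of them. The rules agree at 38 of 67 sample sizes and never differ by more than one toxicity.

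On the first look, starting at n = 3 or n = 4 makes no difference to the stopping probability under beta(0.6, 1.4), because 3/3 leads to at least 3/4 at the next patient. It matters more for the alternatives: beta(0.14, 0.6) and beta(0.4, 1.1) also cross at 2/2, with posteriors of 0.961 and 0.936.

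The list and Table 6 do not agree perfectly. The lower quartile at 0.30 is 48 from the bounds and 41 in the table. The cumulative stopping probability there is nearly flat (0.244 by n = 41, 0.251 by n = 48), so simulation error would explain it, but the protocol does not say that Table 6 was simulated.

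None of this reconciles the stated prior with the bounds.

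**Conclusion.** The concern holds. The stated prior is not the one behind the printed bounds or Table 6. At a true toxicity rate equal to the 30% limit, a rule computed from the stated prior stops with probability 0.525 from the first patient or 0.375 from patient 4, against 0.288 in Table 6 and 0.283 from the printed bounds.

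This rests on a look after every evaluated patient up to 70 and on each printed count holding until the next listed n, the natural reading and one that comes close to Table 6. Confidence is high that the prior is misstated, and moderate that beta(0.6, 1.4) was meant. It should be fixed because the prior is an input to the safety rule, but the operative list is sound enough to use meanwhile.

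**What to change.** 1. Have the sponsor check the prior against its design code and replace the stated one with the prior actually used. Beta(0.6, 1.4) should be entered only if the code confirms it. Table 6 can be checked in the same step, given the 48 against 41 difference.
2. State that looks begin at the fourth evaluated patient, where the printed list starts. From there every candidate prior named above gives the printed bounds.

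Optionally, print the bounds as ranges of n (3 at 4, 4 at 5–6, 5 at 7–8, 6 at 9–11, and so on to 27 at 68–70). This only clarifies the present list.

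The cost is one line for the prior and one for the first look. The bounds and the sample size do not change, and Table 6 is not expected to.

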13.2 Sample Size/ Power Calculation

Assuming that the median progression-free survival (PFS) is 4.9 months and 8.2 months for the everolimus and MK2206 arm, respectively and patients will be randomized with 2:1 ratio into the MK2206 arm and the everolimus arm, then with a total of 75 events (i.e., disease progression or death), we will have an 80% power to detect such a 67% increase in median PFS using one-sided log-rank test and at a 0.10 significance level. The total number of patients to be enrolled will be 105, with 35 on the everolimus arm and 70 on the MK2206 arm. The above calculation also assumes an accrual rate of 4 patients per month, thus it will take 26.3 months to accrue all 105 patients. The maximum study duration will be around 29 months, which include patients' accrual period and a follow-up period. East5 software was used for the sample size/power calculation.

